# 5.6. SPECIFIC IGG TROUGH PK SET

The Specific IgG Trough PK Set includes all subjects in the age group 12 to <76 years following the principles of the SAF for whom at least 1 trough concentration of at least one specific IgG (measured at the central lab) is available. All PK analyses involving specific IgG trough concentrations will be conducted using the Specific IgG Trough PK Set.

Upon review, complete profiles or only certain time points may be excluded from summary of trough concentrations if they have not received proper study medication dosing or had out-of-window sampling.

# 5.7. DENSE PK SUBSET

The Dense PK Subset includes all subjects who received planned doses following the principles of the FAS and for whom at least 1 concentration of total IgGs, IgG subclasses 1-4, or antigen specific IgG levels (anti-pneumococcal capsular polysaccharide, anti-hemophilus influenzae type B, anti-measles, anti-tetanus, anti-cytomegalovirus, and anti-HBs/hepatitis B), measured in the dense sampling period (i.e., after/at the 7th infusion of the 3-week schedule or after/at the 5th infusion of the 4-week schedule, including the predose concentrations) at the central lab will be available. Pharmacokinetic parameter derivation will be done using the Dense PK Subset.

Upon evaluation, subjects may be excluded from the Dense PK Subset if they have not received the required number of study medication doses to achieve steady-state. In other cases, if the number of PK samples is not sufficient to derive PK parameters from standard analytical methods (non-compartmental analysis), an alternative approach (population modelling analysis) may be undertaken.

# 5.8. PROTOCOL DEVIATIONS

Protocol deviations are collected and agreed in the DRM to evaluate protocol deviations considered to have major impact on subject safety or the validity of the study data. Subjects with major protocol deviations will be excluded from the PPS under the assumption that the deviation may have an impact on the efficacy analysis. In some circumstances protocol deviations may result in subject's exclusion from other sets.

Major protocol deviations may include, but not necessarily limited to, the following categories:

- Deviation from Inclusion/Exclusion criteria
- Deviations in study medication administration
- Missed sampling required for dose adjustment
- Use of prohibited medications or treatments
- No diary data collected

• Diary data not reliable

All protocol deviations will be reviewed and decided for major or minor on a regular basis by the Regular Joint Deviation Review Meeting. In case of frequent major protocol deviations according to GCP that may critically compromise the data integrity of the study, the sponsor may also temporally stop the study.

All protocol deviations are reviewed at the DRM with regard to analysis.

All major protocol deviations will be presented in a summary table by protocol deviation category.

A listing of all protocol deviations including major and minor will be also presented and those subjects excluded from analysis sets will be identified in the listing.

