# 3.5. DETERMINATION OF SAMPLE SIZE

A minimum sample size of 50 evaluable subjects was considered sufficient to ensure a power of at least 80% to reject the null hypothesis of an acute serious bacterial infection rate greater or equal to 1.0 by means of a 1-sided test and a Type 1 error of 0.01 assuming a true underlying rate of acute serious bacterial infections of 0.5 per year. About 70 subjects will be enrolled (treated) to account for drop-outs.

The sample size contains at least 50 evaluable male or female subjects (2 to <76 years), including at least 20 pediatric subjects (i.e., young children [2 to <6 years], children [6 to <12 years] or adolescents [12 to < 17 resp. <18 years]) and at least 20 adult subjects.

According to FDA advice from January 12, 2017 for Pediatric Study Plan, age groups are defined as stated in the FDA 2016 guideline differently for the US: The age group of adolescents for the US is restricted to 12 to <17 years and therefore only subjects 2 to <17 years can be enrolled into the group of pediatric subjects (i.e., young children [2 to <6 years], children [6 to <12 years] or adolescents [12 to <17 years].

The above sample size number (to obtain at least 50 subject–years) and inclusion of at least 20 pediatric subjects with the age distribution representative of the subject population follows the advice provided by the EMA (EMA/CHMP/BPWP/94033/2007 rev. 2, 2010) and FDA (FDA, 2008) and FDA (FDA, 2016).

Full pharmacokinetic (PK) characterization at steady state is to be carried out in at least 20 adult subjects and all consenting pediatric subjects (EMA: 6 to <18 years; FDA: 6 to <17 years). Optional sparse sampling will be taken for young children (2 to <6 years).

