### 5.4. PER-PROTOCOL SET

The Per-protocol Set (PPS) includes all subjects who are compliant with the study protocol without any major protocol deviations. Classification of protocol deviations as major or minor will be agreed upon at the Data Review Meeting (DRM) prior to database lock. The decision to carry out any analysis based on the PPS will be evaluated at the DRM. Any analysis based on the PPS will be performed for the primary efficacy endpoint as an additional analysis. Subjects will be analyzed according to treatment received.

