#### 7.5. MEDICATION

All medications will be coded using WHO Drug Dictionary (WHO-DD B3), March 2018.

The number and percentage of subjects taking previous and concomitant other medications (excluding immunoglobulins) will be summarized by ATC Levels 2 and 3.

The number and percentage of subjects taking premedications, to avoid AEs occurring in conjunction with the infusion of IVIg products during the study will also be summarized overall and for each treatment schedule by ATC Levels 2 and 3. These will be identified by a review of the coded medications and include antihistamines, antipyretics, and/or steroids with indication - prophylaxis.

The number and percentage of subjects taking previous and concomitant antibiotic medications will be summarized overall and for each treatment schedule by ATC Levels 2 and 3.

Concomitant antibiotic medication is one of the secondary efficacy endpoints and is described in the Section 8.2.5.

The number and percentage of subjects taking prohibited medication or treatment during the study will be summarized overall and for each treatment schedule by ATC Levels 2 and 3. Prohibited medication or treatment includes passive or active immunizations, administration of plasma preparations, or administration of other immunoglobulins and will be identified by a review of the coded medications.

The number and percentage of subjects taking rescue medication during the study will be summarized overall and for each treatment schedule by ATC Levels 2 and 3. Medication will be ticked as rescue medication by the investigator on the eCRF.

All presentations will be done based on the FAS.

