#### 8.1.2. Sensitivity Analysis of Primary Efficacy Endpoint

The same analysis as described in Section 8.1.1 will be performed based on the PPS. The decision regarding this analysis will be made during the DRM.

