#### 11.2. TREATMENT COMPLIANCE

BT595 is administered intravenously by the instructed study staff. If a subject's treatment deviates from the dosage regimen (e.g., a dosing interruption occurs due to the occurrence of an AE), this will be recorded in the eCRF.

If a subject fails to comply with the dosage regimen (i.e., misses  $\geq 1$  dose[s] of BT595), the subject will be considered to be noncompliant and may be terminated prematurely from the study. The decision to terminate a subject from the study prematurely will be at the investigator's discretion after consultation with the sponsor. Details of any deviations from the dosage regimen will be recorded in the eCRF.

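### The only planned sensitivity analysis of the primary endpoint can drop whole subjects for deviations that follow a serious bacterial infection, which would bias it towards success

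*SAP*

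**What the plan says.** SAP 5.4 limits the per-protocol set (PPS) to subjects who comply with the protocol and have no major deviation. SAP 5.8 makes the subject the unit of exclusion: "Subjects with major protocol deviations will be excluded from the PPS". Its list of categories that may be major includes "Deviations in study medication administration" and the use of prohibited treatments. Major or minor status is settled at deviation review meetings and the DRM, before database lock.

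SAP 11.2 (as protocol 6.3) gives as its example of departure from the regimen the case where "a dosing interruption occurs due to the occurrence of an AE", and classes a subject who misses one or more doses as noncompliant. Infections are recorded as adverse events (protocol 9.1.2.1, SAP 8).

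On prohibited products, SAP 7.5 says: "Prohibited medication or treatment includes passive or active immunizations, administration of plasma preparations, or administration of other immunoglobulins". Protocol 6.10 bars the same products, but only where an emergency does not require them. SAP 7.5 omits that exception.

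For the primary endpoint, SAP 8.1.2 says: "The same analysis as described in Section 8.1.1 will be performed based on the PPS". No other sensitivity analysis is named in SAP 8.1 or protocol 10.5. SAP 5.4 adds: "The decision to carry out any analysis based on the PPS will be evaluated at the DRM". Neither document keeps an SBI that came before the deviation, and neither censors follow-up at the deviation.

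**The concern.** A per-protocol exclusion is harmless to a rate estimate when the reason for it is unrelated to the outcome. Here it may not be. A subject ill with pneumonia or sepsis can miss an infusion because of that illness. The missed dose makes the subject noncompliant, and if the deviation is classed as major, the infection leaves the analysis together with the subject. SAP 5.8 justifies exclusion by the effect a deviation may have on efficacy; in this case the efficacy outcome would have produced the deviation.

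What is at stake is the value of the sensitivity analysis. It should be able to challenge the primary result. An analysis that preferentially loses endpoint events will tend to agree with the primary result or improve on it. Classification, and the choice whether to run the analysis at all, are made in an open-label study when the recorded infections can be known.

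**Working it through.** **Inputs from the documents.** SAP 3.5 aims to "reject the null hypothesis of an acute serious bacterial infection rate greater or equal to 1.0". The test there is one-sided at the 1% level, the assumed true rate is 0.5 per year, and the plan is for at least 50 evaluable subjects (at least 50 subject-years), power of at least 80%, and about 70 enrolled. Planned follow-up ends at about day 379 or 393 (flowchart), that is 379/365 = 1.04 or 393/365 = 1.08 years.

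**Inputs assumed.** p is the probability that one SBI leads to exclusion from the PPS. It combines three steps: the SBI disrupts treatment, the disruption is a deviation, and the deviation is classed as major. The documents give no value, so a range from 0 is shown. The main simulation uses 70 subjects with 1.05 years each.

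**1. The plan's own figure.** With 50 subject-years the null mean is 50 events. The exact one-sided test rejects at 33 or fewer: P(X ≤ 33 | mean 50) = 0.0070. Power at a rate of 0.5 is P(X ≤ 33 | mean 25) = 0.950. The stated power of at least 80% is met.

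**2. Rate on the PPS.** Let X, the SBI count over T years, be Poisson with mean LT, and let a subject stay in the PPS with probability (1−p)^X. Then

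- expected events kept: E[X(1−p)^X] = LT(1−p)·exp(−LTp)
- expected years kept: T·E[(1−p)^X] = T·exp(−LTp)
- ratio: L(1−p)

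Exclusion unrelated to SBIs cancels from the ratio. In simulation, 10% unrelated exclusion with p = 0 returned 0.50 and 1.00 for true rates of 0.5 and 1.0.

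**3. Results** (exact Poisson 99% upper limit below 1.0 counted as a pass):

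| p | PPS rate, true 0.5 | PPS rate, true 1.0 | PPS pass at true 1.0 |
|---|---|---|---|
| 0 | 0.50 | 1.00 | 0.7% |
| 0.1 | 0.45 | 0.90 | about 5.5% |
| 0.2 | 0.40 | 0.80 | about 21% |
| 0.4 | 0.30 | 0.60 | about 74% |

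With 50 subjects and 1 year each, the pass rates at a true 1.0 are 0.7%, 4.0%, 20.6% and 74.6% for p = 0, 0.10, 0.25 and 0.50.

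**4. Example at the design values.** 25 events in 50 subject-years give a rate of 0.50 and an exact 99% upper limit of 0.786. Dropping five subjects with one SBI each leaves 20 events in 45 subject-years: 20/45 = 0.444, upper limit 0.736.

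**5. Censoring at the deviation instead.** The infection that led to the deviation is counted, and time stops there. Under a common Poisson rate this returned 0.50 and 1.00 for true rates of 0.5 and 1.0, with under 1% false passes at 1.0. If rates vary between subjects (gamma, assumed relative variance 1, p = 0.4, true mean 1.0), write a = pT = 0.42:

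- censoring: [a/(1+a)] / ln(1+a) = (0.42/1.42)/0.351 = 0.84
- whole-subject exclusion: (1−p)/(1+a) = 0.6/1.42 = 0.42

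**The case against.** Four points carry weight.

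- The categories in SAP 5.8 only may be major. A reader might infer that every missed infusion removes a subject and that the PPS rate is therefore biased low. The documents do not go that far: status is decided case by case, and no passage says that an SBI leads to a missed dose. This stands, so the bias is conditional. Nothing in writing, however, prevents an SBI-driven deviation from being classed as major, and SAP 5.4 requires compliance while SAP 11.2 calls a missed dose noncompliance.
- The prohibited-product route is weak. Protocol 6.10 exempts emergency use, and SAP 7.5 defines a medication summary, not an exclusion rule. This stands. The remaining risk is that SAP 7.5 drops the exemption while protocol 10.2 detects prohibited medication from drug codes, which do not show an emergency.
- The SAP offers some visibility. SAP 8.1.1 tabulates SBI counts in subjects who missed an infusion or discontinued, and requires a description of each SBI. SAP 7.1 summarises exclusions by reason, and SAP 5.8 lists excluded subjects. A careful reader could see the problem, but these outputs give no rate, limit or test.
- Net direction is not certain. Absent or unreliable diary data are also listed as possible major deviations, and removing subjects whose infections were under-recorded could raise the PPS rate.

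A reader might also infer that the trial's conclusion is at risk. It is not: the primary test uses the full analysis set (FAS), and the PPS analysis is additional and cannot rescue a failed primary test.

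**Conclusion.** The point holds in conditional form. The only planned sensitivity analysis of the primary endpoint can exclude subjects for deviations that follow an SBI, mainly through missed infusions. If SBIs make exclusion more likely, the PPS rate falls by the factor (1−p), and the analysis leans towards success: even p = 0.1 moves its false-pass rate at a true 1.0 from 0.7% to about 5.5%. With p = 0 there is no such bias. The sizes rest on an assumed p, on Poisson counts with a common rate, and on how the review meetings classify deviations. The primary FAS test and its error rate do not change. This is a change that should be made because a robustness check that can select on its own outcome gives little reassurance; it is not a flaw in the confirmatory test.

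**What to change.** In SAP 5.4, 5.8 and 8.1.2:

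- Exclude whole subjects only for eligibility deviations.
- For later major deviations, keep the subject and count SBIs and subject-days up to the first such deviation. Never drop an SBI with onset on or before it. Because SAP 8.1.1 dates onset by diagnosis, state how an SBI is handled when the illness led to the missed infusion but was diagnosed afterwards.
- Fix the rules for major status in advance and without regard to SBI outcome.
- Run the analysis whatever the DRM decides.
- Reconcile SAP 7.5 with protocol 6.10 on emergency use of the listed products.

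The cost is SAP wording and one derived date per subject. The PPS rate may become less favourable. Some downward bias remains if infection rates differ between subjects (0.84 for a true 1.0 in the gamma example, against 0.42 with whole-subject exclusion), so the result should be read beside the FAS analysis.

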# 6. GENERAL ASPECTS FOR STATISTICAL ANALYSIS

#### 6.1. GENERAL METHODS

Data from all subjects collected in this study will be documented with the help of subject data listings. Summary tables will be provided for all patients, except screen failures.

Generally, descriptive statistics will be provided by treatment schedule (3- or 4- week) and overall. Additionally by dosage and by observation time (visit), if applicable. Only scheduled visits/time points will be presented in summary tables. Data from unscheduled visits will be listed only.

Quantitative (continuous) data - absolute values and changes from baseline, where appropriate - will be summarized with number of observations (n), arithmetic mean, standard deviation (SD), median, minimum, and maximum. Confidence intervals, 25th percentile and 75th percentile will be added where applicable.

Qualitative (categorical) data will be summarized using number of observations (n), and frequency and percentages of subjects. Unless stated otherwise, the calculation of percentages will be based on the total number of subjects in the set of interest. Thus, counts of missing observations will be included in the denominator and presented as a separate category. Confidence intervals will be added, where applicable.

All data will be listed for the All Subjects Enrolled Set, sorted by subject number and time of occurrence (visit, start of event) whereas treated subjects will be sorted above screening failures.

Shells for summary tables, figures, and subject listings are described in a separate document, which is seen as an Appendix to the SAP. Templates for each unique table, figure, and listing are provided. These provide only a draft indication of the content and appearance of the tables, figures, and listings, and the final output may vary in appearance from these templates.

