#### Definition of Baseline

Baseline will be defined as the last available value before the first infusion of study medication and may be any visit between screening and day 1 (including the baseline visit [V2]) and unscheduled visit.

Duration of concomitant antibiotic treatment

If medication starts before date of first infusion (Visit 2, Day 1): Duration of concomitant antibiotic treatment [days] = Date of stop of antibiotic treatment – Date of first infusion +1.

If medication starts at/after date of first infusion (Visit 2, Day 1):

Duration of concomitant antibiotic treatment [days] = Date of stop of antibiotic treatment – Date of start of antibiotic treatment + 1

Duration of infusional AE

Duration of AE [hours] = (Date/time of stop of AE – Date/time of start of AE)

Duration of noninfusional AE

Duration of AE [days] = Date of stop of AE – Date of start of AE + 1

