### Coagulation

- Fibrinogen
- Prothrombin time, international normalized ratio
- Partial prothrombin time

	l
Urina	IVSIS
••••••	.,

Urmany	
•	рН
•	Qualitative for blood
٠	Leukocytes
٠	Protein
•	Glucose
٠	Ketone bodies
٠	Bilirubin
٠	Urobilinogen
•	Nitrites
•	Osmolality
•	Urine sediment microscopy (Erythrocyte casts, Hemoglobin urinary casts, leukocyte urinary
	casts, epithelial urinary casts (tubular urinary casts), granular urinary casts)
•	Hematuria
Hemol	ysis parameter
•	Coombs test
•	serum haptoglobin
•	plasma-free hemoglobin
•	urine hemosiderin

Safety laboratory assessments will be categorized with respect to the local laboratory specific reference ranges as normal/abnormal. Abnormal values will be further classified with respect to clinical relevance: not clinically significant (NCS) high or low or clinically significant (CS) high or low. All laboratory results will be listed with International System of Units (SI). The number and proportion of subjects with at least 1 CS abnormal value and the number of CS abnormal values will be summarized by laboratory test categories: clinical chemistry, hematology, coagulation, urinalysis by baseline and all post-baseline visits. Changes over time will be described by means of "shift-tables", comparing the post-baseline values versus baseline value. The data will be listed. Values below or above the reference values in the data listings will be flagged. All laboratory values will be converted into standard units (SI units, if applicable) for evaluation and presentation reasons. Presentations will be done by scheduled visits as described in the flow chart, Section 3.8.

For the definition of baseline value refer to Section 6.2.

All data including pregnancy test results will be listed.

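### Apart from positive-Coombs follow-up, unscheduled post-baseline laboratory values are left out of the clinically significant abnormality counts, shift tables and hemolysis summaries

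*SAP*

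**What the plan says.** SAP 6.1 sets the default for the whole analysis: "Only scheduled visits/time points will be presented in summary tables. Data from unscheduled visits will be listed only". SAP 11.4 repeats it for laboratory data: "Presentations will be done by scheduled visits as described in the flow chart, Section 3.8".

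The outputs affected are these:

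- **CS counts (SAP 11.4).** "The number and proportion of subjects with at least 1 CS abnormal value and the number of CS abnormal values will be summarized" for the categories "clinical chemistry, hematology, coagulation, urinalysis by baseline and all post-baseline visits".
- **Shift tables (SAP 11.4).** These are described as "comparing the post-baseline values versus baseline value". No worst-post-baseline or any-time shift is defined.
- **Hemolysis summaries (SAP 11.7.1).** Results are tabulated by scheduled visit, and further evaluations after a positive Coombs test are added. A composite of a hemoglobin drop of at least 1.0 g/dL, haptoglobin below normal and a rise in lactate dehydrogenase (LDH) is to be summarized. The same composite with a drop of at least 2.0 g/dL, or hemolysis reported as an event of special interest, leads to a narrative.

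For the listings, SAP 11.4 says "Values below or above the reference values in the data listings will be flagged". SAP 6.3 and Protocol 10.3 both say that all available data go into the analyses and are summarized where possible.

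**The concern.** A table of subjects with at least one CS value is meant to answer whether the abnormality ever occurred on treatment. Restricting it to scheduled visits answers a narrower question, and nothing in its description tells the reader so. Repeat and for-cause tests are unscheduled by nature, so the restriction acts on draws taken because someone wanted to look again.

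Hemolysis is where it matters most. It is an adverse event of special interest and a mandatory withdrawal criterion (Protocol 9.3.1), yet haptoglobin has very few scheduled post-baseline time points. A summary that ignores off-schedule haptoglobin would rest on little more than the closing visit for most subjects.

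**Working it through.** The plan gives no figure on this point, so there is nothing to reproduce. The check sets the texts side by side and then counts samples.

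**1. Which rule governs.** SAP 6.1 and the scheduled-visit sentence in SAP 11.4 point to exclusion. The phrase on all post-baseline visits in SAP 11.4, SAP 6.3 and Protocol 10.3 point to inclusion. Protocol 10.7 puts no scheduled-only limit on laboratory summaries, and SAP section 13, which lists departures from the protocol, does not mention one. The specific sentences in 6.1 and 11.4 are the ones a programmer would follow.

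**2. Direction.** SAP 6.1 bases percentages on all subjects in the set unless stated otherwise, so the denominator does not change when a value is dropped. Only the numerator can change, and only downward.

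**3. Hemolysis.** Under SAP 11.7.1, haptoglobin and Coombs tests are scheduled at screening and closing, with extra tests at V3 and V4 for the first 10 patients. Of about 70 subjects, about 70 − 10 = 60 have one scheduled post-baseline haptoglobin, at closing. Hemoglobin and LDH belong to the routine panels taken at every infusion visit. For these subjects the composite can therefore be met between baseline and closing only through an off-schedule haptoglobin. If the Coombs test is positive, that result enters the summaries. If haptoglobin was drawn for cause and Coombs is negative, no exception applies. The SAP flow chart (3.8) does not show the V3/V4 hemolysis tests that the protocol flow chart shows, so even their status as scheduled is unclear.

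**4. The AE route.** Protocol 9.2.1.4 requires out-of-range values judged clinically relevant to be recorded as AEs at any sampling date after consent, and SAP 11.3 tabulates treatment-emergent AEs by onset, not by visit. There are two gaps:
- A value that is a sign of an AE already reported does not become an AE of its own (Protocol 9.2.1.4).
- Extra safety visits for abnormalities at the last study visit (Protocol 9.3.4) take place after the treatment-emergent window has closed (SAP 11.3).

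**5. Size.** With about 70 treated subjects (SAP 3.5), one missed subject is 1/70 = 1.4 percentage points. Safety is also stratified by age (SAP section 11); with the minimum of 20 pediatric subjects, one is 1/20 = 5 points in that subtotal. These are the weights of one subject. How many are affected cannot be derived.

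**6. How often a worst value might be unscheduled.** Scheduled post-baseline safety samples per completer (Protocol 7.1) are the end of the first infusion, the later infusion visits and closing:
- 3-week schedule: 1 + 17 + 1 = 19
- 4-week schedule: 1 + 13 + 1 = 15

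Assume u unscheduled draws that are no more abnormal than scheduled ones. Both u and this equality are assumptions; the documents give neither. The chance that a subject's worst value is unscheduled is then u/(u + 19) or u/(u + 15):

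| u | 3-week schedule | 4-week schedule |
|---|---|---|
| 1 | 1/20 = 5.0% | 1/16 = 6.3% |
| 3 | 3/22 = 13.6% | 3/18 = 16.7% |

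Draws prompted by symptoms or an earlier abnormal result would raise these figures by an unknown amount. The calculation applies to the routine panels, not to haptoglobin.

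**The case against.** A reader might infer that unscheduled values disappear from every summary table and that the worst on-treatment results are systematically lost. The documents do not support that. Positive-Coombs follow-up is summarized. Narratives cover the 2.0 g/dL composite and reported hemolysis. Clinically relevant values normally reach the AE tables, and if one is a sign of an AE already reported, that AE is itself counted. With 15 to 19 scheduled samples per completer, a repeat test prompted by a CS scheduled value concerns a subject who is already counted. Nothing in the documents shows that unscheduled draws hold the extremes. All of this stands and limits the point to subjects whose only qualifying value is unscheduled.

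A reader might also see bias in the baseline definition, because baseline "may be any visit between screening and day 1 (including the baseline visit [V2]) and unscheduled visit" while the post-baseline side of a shift may not be unscheduled. That does not hold. Taking the last value before first infusion is an ordinary timing rule, it is also in Protocol 10.3, and no direction of bias follows from it.

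Two further objections have some weight. Safety results are descriptive, and the table shells, which are a separate document, may already settle how any-time rows are built. But the shells are described in SAP 6.1 as draft indications of content, so the rule belongs in the SAP text. A worst-value shift table is an addition rather than a repair, though it is the natural companion to an any-time count.

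**Conclusion.** The point holds for the CS counts, the shift tables and the hemolysis summaries, apart from positive-Coombs follow-up. As the SAP reads, a subject whose only CS value or only qualifying haptoglobin result is unscheduled is not counted in them. The direction is certain: subject counts can only be understated. The amount is unknown, and 1.4 percentage points should not be read as an estimate of bias. The exposure is modest for the routine panels, which are sampled often. It is most serious for the 1.0 g/dL hemolysis composite, which depends on a test scheduled once after baseline for most subjects.

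This rests on SAP 6.1 and the scheduled-visit sentence in 11.4 prevailing over the inclusive wording in 6.3 and elsewhere in 11.4. If the inclusive wording is what was intended, the defect is a contradiction that needs the same correction. The efficacy conclusion is not affected.

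**What to change.** - Keep by-visit summaries on scheduled visits.
- In SAP 11.4, state that the any-time post-baseline CS counts use all post-baseline values, including unscheduled ones, and add a baseline-to-worst-post-baseline shift table on the same basis.
- In SAP 11.7.1, state that summaries of the hemolysis composite, at both the 1.0 and the 2.0 g/dL hemoglobin drop, use all post-baseline values whatever the Coombs result. This also settles the status of the V3/V4 tests.
- Reconcile SAP 6.1 with 6.3 and with the all-post-baseline-visits wording in 11.4, so that one rule remains.

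The cost is a few sentences and a small amount of programming; no new data are needed. The number of CS values will then include repeat tests of the same episode, so the number of subjects is the figure to interpret.
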